2) The pooled standard deviation for the changes in hemoglobin level was 15 g/L.
3) Non-inferiority margin is 5 g/L.
4) The significance level (two-sided, in accordance with FDA recommendations) is 95%, which corresponds to the type I one-sided error 0.05.
5) Power of the study is 80%, which corresponds to the type II error 0.20.
6) Statistical hypotheses – evidence of a non-inferior efficacy:
H0: $\mu_{A} - \mu_{B} \le 5.0$ H1: $\mu_{A} - \mu_{B} > 5.0$
7) The ratio between the study and control group sizes is 1:1
8) Interim analysis will be performed at 70% of the total sample size

 
9) O'Brien-Fleming alpha-spending function will be used with 80% power for efficacy boundary that will correspond to the following critical values for t-test: 2,628 for interim analysis (corresponds to p=0,005) and 1,976 for final analysis (corresponds to p=0,0245);
 

Calculation was performed using the clinfun package of Microsoft R Open software (available at https://mran.microsoft.com – Microsoft R Application network), that uses the group sequential design approach for the calculation of fixed sample sizes for the interim and final analysis.
According to the output from the clinfun package, 143 subjects per group (286 subjects in total) should complete the study in order to

confirm non-inferiority. 200 (100 per group) subjects should have evaluable data to perform interim analysis. Taking 15% withdrawal rate into account, one need to randomize 336 subjects (168 subjects per group). Taking 30% screening failure rate, up to 480 subjects should be screened to achieve target randomization.
should be serected to achieve target randomization.

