- 12) Non-inferiority margin is 5 g/L.
- 13) The significance level (two-sided, in accordance with FDA recommendations) is 95%, which corresponds to the type I one-sided error 0.05.
- 14) Power of the study is 80%, which corresponds to the type II error 0.20.
- 15) Statistical hypotheses evidence of a non-inferior efficacy:

- 16) The ratio between the study and control group sizes is 1:1
- 17) Interim analysis will be performed at 70% of the total sample size
- 18) O'Brien-Fleming alpha-spending function will be used with 80% power for efficacy boundary that will correspond to the following critical values for t-test: 2,628 for interim analysis (corresponds to p=0,005) and 1,976 for final analysis (corresponds to p=0,0245);

Calculation was performed using the clinfun package of Microsoft R Open software (available at https://mran.microsoft.com – Microsoft R Application network), that uses the group sequential design approach for the calculation of fixed sample sizes for the interim and final analysis. According to the output from the clinfun package, 143 subjects per group (286 subjects in total) should complete the study in order to confirm non-inferiority. 200 (100 per group) subjects should have evaluable data to perform interim analysis. Taking 15% withdrawal rate into account, one need to randomize 336 subjects (168 subjects per group). Taking 30% screening failure rate, up to 480 subjects should be screened to achieve target randomization.

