- 2) A pooled standard deviation for the changes in hemoglobin levels was 15 g/L.
- 3) The non-inferiority margin is 5 g/L.
- 4) The significance level (two-sided, according to the recommendations by the Food and Drug Administration) is 95%, which corresponds to a one-sided type I error of 0.05.
- 5) The study power is 80%, which corresponds to a type II error of 0.20.
- 6) Statistical hypotheses are the demonstration of non-inferiority:

$$\mu A - \mu B > 5.0$$

- 7) The ratio between the test and control group sizes is 1:1.
- 8) The interim analysis will be conducted when 70% of the total sample size is reached.
- 9) The O'Brian-Fleming alpha-spending function will be applied with 80% power for the efficiency frontier, which will satisfy the following critical values of the t-test: 2.628 for the intermediate analysis (corresponding to p = 0.005) and 1.976 for the final analysis (corresponding to p = 0.0245).

STATISTICAL ANALYSIS PLAN

Calculations were performed using the clinfun package of the R software, in which the calculation of a fixed sample size for interim and final analyses was performed using the group sequential design.

According to the data obtained with the clinfun package, 143 subjects in each group (total: 286 subjects) should complete the study to confirm the hypothesis of non-inferiority. For the interim analysis, data for 200 subjects (100 in each group) that are suitable for analysis should be obtained. Taking into account the frequency of premature discontinuation of the study, which is 15%, it is necessary to randomize 336 people (168 people in each group). Taking into consideration the withdrawal rate based on the results of the screening that equals to 30%, about 480 people should undergo screening to achieve the target level of randomization.

3. General analysis values

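### The critical values 2.628 and 1.976 are not those of the O'Brien-Fleming spending function the plan names, so name and numbers define two different rules for the primary claim

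*Protocol*

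**What the plan says.** Three places name the method and attach the same pair of critical values to it.

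- Protocol 9.3 item 18: "O'Brien-Fleming alpha-spending function will be used with 80% power for efficacy boundary that will correspond to the following critical values for t-test: 2,628". The full pair there reads "2,628 for interim analysis (corresponds to p=0,005) and 1,976 for final analysis (corresponds to p=0,0245".
- Synopsis, sample size justification, item 9: "O'Brien-Fleming alpha-spending function will be used with 80% power for efficacy boundary", with the same two values.
- SAP 2.3 item 9: "The O'Brian-Fleming alpha-spending function will be applied with 80% power for the efficiency frontier", with "2.628 for the intermediate analysis (corresponding to p = 0.005) and 1.976 for the final analysis (corresponding to p = 0.0245".

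On timing, protocol 9.3 says "Interim analysis will be performed at 70% of the total sample size" and "200 (100 per group) subjects should have evaluable data to perform interim analysis"; 200 of 286 is 69.9%. SAP 2.3 and SAP section 11 also use 200. Protocol 9.2 and the interim analysis row of the synopsis set the look at no fewer than 240 patients with primary endpoint data, which is 83.9% of 286.

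SAP 8.1 takes the confidence level at each analysis from SAP 2.3, so item 9 of that section is the decision rule for non-inferiority.

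**The concern.** The plan presents the two numbers as what the named function produces. If it does not produce them, SAP 2.3 holds two rules and does not say which prevails. A statistician who programs the named function uses 2.438 at a 70% look, an interval of about 98.5%. One who copies the printed number uses 2.628, about 99.1%. The rules also part at the end: a final statistic between 1.976 and 2.000 succeeds under the printed value and fails under the spending function.

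The trial is open-label (protocol 4.4.2), the sponsor knows the allocation (protocol 4.10), and the sponsor decides on stopping from the interim results (protocol 9.2, SAP section 11). A threshold with two readings should not still be open when those results are seen.

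**Working it through.** **Inputs.** Margin 5 g/L, SD 15 g/L, true difference 0, 1:1 allocation, 80% power, 143 per group, look at t = 0.70 (protocol 9.3, SAP 2.3). One assumption: alpha is one-sided 0.025. The plan states a two-sided 95% level and a one-sided error of 0.05 together, but its figures reproduce only with one-sided 0.025.

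**Method.** Let Z1 and Z2 be the interim and final statistics for (test minus reference + 5)/SE. They are bivariate normal with correlation √0.70. One-sided alpha is 1 − P(Z1 ≤ z1, Z2 ≤ z2) with the difference at the margin.

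**1. Reproducing the plan's figures.** In the family z = c·t^(−d), d = 0.5 is the classical O'Brien-Fleming boundary. The printed pair implies

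d = ln(2.628/1.976) / ln(1/0.70) = 0.2851/0.3567 = 0.799.

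Solving for c with d = 0.80 and alpha 0.025 gives 2.628 and 1.976. For 80% power the printed pair needs a drift of 2.8097, so n = 2·(15 × 2.8097/5)² = 142.1, rounded up to 143 per group. The look then falls at 0.70 × 143 = 100 per group. The printed boundary, the 143 and the 100 are mutually consistent.

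**2. What the named method gives at t = 0.70**

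| Boundary | Interim | Final | Interim one-sided p (normal) |
|---|---|---|---|
| Printed (fits d = 0.80) | 2.628 | 1.976 | 0.0043 |
| O'Brien-Fleming spending | 2.438 | 2.000 | 0.0074 |
| Classical O'Brien-Fleming (d = 0.5) | 2.400 | 2.008 | 0.0082 |

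The spending function is α(t) = 2 − 2Φ(z/√t) with z the upper 0.0125 normal quantile; α(0.70) = 0.0074.

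**3. Could another stated input rescue the label?** No. The spending function gives 2.186/2.036 at 240/286 and 2.681/1.980 at 200/336. At t = 0.70 with one-sided 0.05 it gives 2.072/1.702. With d = 0.5 the printed ratio would need t = (1.976/2.628)² = 0.565, which is stated nowhere.

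**4. Error rate of the printed pair.** One-sided alpha is 0.02498 at t = 0.70 and 0.0243 at 240/286.

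**5. Consequences when the products are equal, 143 per group.** The drift is 5/(15·√(2/143)) = 2.819, so the mean of Z1 is 2.819 × √0.70 = 2.358.

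- Crossing at the look: 1 − Φ(2.628 − 2.358) = 39%; 1 − Φ(2.438 − 2.358) = 47%; classical 48%.
- Power: 80.2% printed, 79.9% spending, 79.8% classical. A full 80% under either O'Brien-Fleming form needs 144 per group.
- Different final verdict, printed against spending: Z1 between 2.438 and 2.628 and then Z2 ≤ 1.976, about 0.3%; Z1 ≤ 2.438 and Z2 between 1.976 and 2.000, about 0.6%; total about 0.9%.
- Estimate needed to cross at the look: SE = 15·√(2/100) = 2.12 g/L, so the difference must favour the test product by 2.628 × 2.12 − 5 = 0.57 g/L (printed) or 2.438 × 2.12 − 5 = 0.17 g/L (spending).

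**The case against.** The strongest reply is that only the label is wrong. SAP 8.1 points to SAP 2.3, which prints the numbers, and all three places agree on them. The pair controls alpha, is stricter at the look and supports the stated 143 per group. On the t distribution the one-sided p-values are 0.0046 (198 df) and 0.0246 (284 df), close to the printed 0.005 and 0.0245. All of this stands, and it limits the harm. It does not remove the contradiction, because the section SAP 8.1 relies on contains the method name as well as the numbers and gives neither precedence.

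Three stronger readings are tempting and are not supported:

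- **Alpha is inflated.** An O'Brien-Fleming look followed by the printed 1.976 would give 0.0262 (spending) or 0.0266 (classical). No text plans that mixture; the values are printed as a pair.
- **About 7.5% of trials would be decided differently.** That is the chance, with equal products, that the interim statistic lies between 2.438 and 2.628. It concerns whether the trial could stop early, and stopping is at the sponsor's discretion. Nearly all of these trials still succeed at the end.
- **The 80% power was entered as the boundary exponent.** The odd phrase about power for a boundary fits this, but the software call is not shown. With alpha fixed, a two-look boundary has one free parameter, so matching both values is one agreement, not two. The mismatch does not depend on this explanation.

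**Conclusion.** The point holds as an inconsistency in the decision rule for the primary endpoint. At a 70% look and one-sided 0.025, the O'Brien-Fleming spending function gives 2.438/2.000, not 2.628/1.976. The printed pair is a valid boundary under the wrong name.

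The size is modest: 39% against 47% for the chance of being able to stop at the look, about 0.9% for a different final verdict, and 0.3 percentage points of power. These figures assume equal products, SD 15 g/L, 143 evaluable patients per group, normal approximations and a look at 70%. The last is itself unsettled, since protocol 9.2 and the synopsis interim row say 240 patients. It still needs correcting because it sets the threshold for the primary claim and cannot credibly be settled after interim results are known.

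**What to change.** Before the look, and with identical wording in the synopsis, protocol 9.3 and SAP 2.3:

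1. Reconcile the size of the look: 240 in protocol 9.2 and the synopsis interim row, 200 in protocol 9.3 and SAP section 11. The correct boundary depends on it.
2. Then choose one rule.
   - (a) Keep 2.628/1.976 for a look at 70%. Delete the O'Brien-Fleming spending label and the phrase giving the boundary 80% power, and describe it as a power-family boundary with exponent 0.80. Alpha, power and N stay as they are. This description fits only a 70% look.
   - (b) Keep O'Brien-Fleming spending at one-sided 0.025 and compute the values at the actual information fraction: 2.438/2.000 at 70%, about 2.186/2.036 at 240/286. For a 70% look, restate power at 143 per group as 79.9%, or plan 144 per group if a full 80% is required. For another fraction, recompute the power.

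The cost is wording and a few numbers in three places, plus the alignment of the look size. Option (a) needs no extra patients; nor does (b) if 79.9% is accepted.

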## 9.4 Applied significance level of the clinical trial

All the statistical tests within this study will be performed at 95% confidence level (threshold value p to confirm stastistical significance is less 0.05). The two-sided statistical criteria will be used for all other studied parameters.

## 9.5 Clinical study termination criteria

The trial may be terminated under conditions described in Section 4.8of this protocol.

## 9.6 Accounting for missed, unanalyzable, and questionable data

During the monitoring visits to the trial sites, the clinical trial specialists (monitors) authorized by the Sponsor will analyze eCRFs for the data completeness. In the absence of data on CRFs and the availability of relevant information in the primary documentation, questions for investigators and regulations to address inconsistencies will be formulated.

At the database check, the expert in statistics authorized by the Sponsor, and the data control and processing managers will analyze the trial results for questionable, missed, and unanalyzable data, which might be the basis for the questions for investigators.

If possible, the investigators will eliminate the errors identified in eCRFs and inform the Principal Investigator and authorized representatives of the Sponsor hereof. In case the identified data errors cannot be eliminated after the completion of the patients participation in the trial, the analysis of the resulting parameter sensitivity to questionable data will be conducted in the statistical analysis. Information about the missed, questionable, and unanalyzable data will be summarized in the final clinical trial report.

A method of filling in the missing data based on maximum likelihood estimation, MLE for the primary end-point will be applied if needed[64].

Analysis of the rest of endpoint types and other parameters will be performed only on the basis of the actually available information without filling in the missing data in view of short duration of the clinical trial.

## 9.7 Procedures for reporting any deviations from the original statistical plan

All deviations from an initial statistical plan must be described and justified in a protocol amendment and/or a final trial report (in the latter case, a statistical analysis plan developed before the start of a final statistical analysis must contain a list of those deviations with justification for the reasons thereof).

## **9.8** Procedures for clinical trial participants selection with a view to analysis

The following data sets will be used for analysis:

• The intention-to-treat (ITT) population: all randomized subjects who were administered at least one dose of the investigational product or comparator and who have hemoglobin level data both before and after treatment with the investigational product and the reference product.

In accordance with principles of ICH E9 guidelines, the ITT population will be considered to be a population for statistical analysis.

- The per protocol (PP) population: all randomized subjects who have completed participation in the trial in accordance with the protocol (have completed the prescribed period of treatment and follow-up without significant deviations from the protocol).
- The safety population (safety): All randomized subjects who received at least one dose of the study drug/comparator drug and completed at least one safety parameters evaluation visit. Unlike the ITT population, the safety population will be analyzed depending on actually received treatment rather than not only prescribed (in the case of difference detection between the prescribed and received therapies).

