Ferrum Lek® (iron (III) hydroxide polymaltosate), 100 mg of tablets (Lek d.d., Slovenia), compared to MALTOFER® (Vi Switzerland), in the treatment of patients with mild and iron-deficiency anaemia.Study objectivesMain Objective: To assess the non-inferiority of the therapeutic efficacy of Lek® 2 tablets daily (200 mg), via assessing the effect on her level in the blood (g/l) after 12 weeks of treatment for pati- iron-deficiency anemia of mild and moderate severity compa MALTOFER® 2 tablets daily (200 mg) during the same per Secondary objectives:	
To assess the non-inferiority of the therapeutic efficacy o Lek ® 2 tablets daily (200 mg), via assessing the effect on her level in the blood (g/l) after 12 weeks of treatment for pati- iron-deficiency anemia of mild and moderate severity compa MALTOFER ® 2 tablets daily (200 mg) during the same per Secondary objectives:	hewable for S.A.,
Lek ® 2 tablets daily (200 mg), via assessing the effect on her level in the blood (g/l) after 12 weeks of treatment for pati- iron-deficiency anemia of mild and moderate severity compa MALTOFER ® 2 tablets daily (200 mg) during the same per Secondary objectives:	
	noglobin ents with ared with
Assessment of safety of Ferrum Lek ® 2 tablets daily (2)	
compared with MALTOFER ® 2 tablets daily (200 mg), frequency, characteristics, intensity and relationship to t received of AEs.	via the
Number of study sites20 sites in the Russian Federation.	

Number of subjects	It is planned to randomize 336 patients (168 patients in each treatment group) considering that no more than 15% of them will drop out before the end of study per protocol.
	Randomization will be stratified by two factors:
	- Gender (male vs female);
	- Hb level (80–94 g/L vs 95–110 g/L)
	Thus, it is necessary to receive data from at least 286 patients (143 patients in each treatment group) who completed the study according to protocol.
Duration of the study	Subject enrollment – not longer than 9 months. Treatment – 3 months (12 weeks). Follow-up visit (by phone) – 14 days after the last planned visit to the study cite. Total study duration – not more than 12 months.
Study design	A phase III, open-label, active-controlled, randomized, multicenter, prospective, comparative, parallel-group study (in the Russian Federation).

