## 5.3 Exclusion criteria

#### 5.3.1 Terms and conditions for the subjects exclusion from the study

The subjects may be excluded from the study on their own free will at any moment, without giving any reason, as well as upon decision of the Investigator or Sponsor in cases when continuation of the participation may inflict harm to the patient's health and/or life. In addition, the patient must be excluded in the cases listed below:

- 1. Negative trend of the disease
- 2. The Ethics Committee, regulatory authorities or Sponsor terminate the study or participation of the specific study site for any reason.
- 3. The Investigator's decision to withdraw the patient from the study in the interests of the patient.
- 4. Withdrawal of the informed consent (unwillingness of the patient to continue his/her participation in the study).
- 5. Serious deviation from the study protocol;
- 6. Individual intolerance of study drugs;
- 7. Clinically significant adverse event or serious adverse event related to investigational drug;
- 8. Patient's non-compliance;
- 9. False inclusion (e.g., the patient was included in breach of the inclusion/non-inclusion criteria);
- 10. The patient complies with the non-inclusion criteria during the study;
- 11. Patient receives/needs additional treatment, which may influence the study results or patient's safety;
- 12. Other conditions or events which, in the Investigator's opinion, require the patient's exclusion from the study.

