## 7 Assessment of efficacy

## 7.1 Methods and periods for registration of efficacy parameters

The efficacy of the study therapy is based on laboratory and clinical data.

Laboratory parameters for effectiveness evaluation will be collected at screening visits (Visit 0), Visit 2, Visit 3 and the final visit (Visit 4):

- Complete blood count (hemoglobin);
- Iron metabolism indices (ferritin, transferrin, transferrin saturation percentage, serum iron).

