#### 9.1.2 Analysis of the primary efficacy endpoint

#### Primary efficacy endpoint:

• Changes in blood haemoglobin level (g/L) after 12-weeks of iron-deficiency anaemia treatment (during the final visit), as compared with the baseline value (the screening visit) between the study groups.

Analysis of covariance (ANCOVA) will be used as the main method of assessment of the primary endpoint, with baseline haemoglobin value being a covariate and four fixed factors (treatment group, gender, weight and baseline Hb level (80–94 g/L vs 95–110 g/L). Unrestricted least significant differences (LSD) method will be applied to the ANCOVA results with the calculation of least-square (LS) means with 95% CI for LS means for the difference between the study groups. Non-inferiority will be confirmed if the upper limit of the two-sided 95% confidence interval for LS mean will not exceed the pre-defined non-inferiority margin of 5 g/L.

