ITP	Iron transport proteins 1 and 2
RE	Reticuloendothelial (cells)
RES	Reticuloendothelial system
SBP	Systolic blood pressure
SAE	Serious adverse event
SOD	Superoxide dismutase
SOP	Standard operating procedure
TF	Transferrin
TfR	Transferrin receptor
FL	Federal law
Full name	First name, Patronymic, Last name
CNS	Central nervous system
Ср	Ceruloplasmin
RR	Respiration rate
HR	Heart rate
ECG	Electrocardiography

1. Introduction

This study is planned and carried out to demonstrate the non-inferiority and safety of Ferrum Lek[®] (iron (III) hydroxide polymaltosate), 100 mg chewable tablets (Lek d.d., Slovenia), compared to MALTOFER[®] (Vifor S.A., Switzerland), in subjects with mild and moderate iron deficiency anemia.

The objective of this Statistical Analysis Plan is more detailed, compared to Section 9 of the study protocol, description of the main principles of the protocol-based statistical analysis, description of the primary and secondary endpoints analysis methods as well as other data obtained during the study.

This Plan stipulates for conformance of the scheduled and conducted statistical analysis to the study protocol, including the definition of the analysis data sets, transformations and calculations for the endpoints, observations quantity needed, etc.

2. Study objectives and design

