4.3.2. ITT population receiving treatment

All randomized subjects who received at least one dose of the investigational medicinal product and completed at least one efficacy parameters evaluation visit.

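### The method for missing Week 12 haemoglobin is not specified, the two documents define ITT differently, and the per-protocol set has no stated role

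*Protocol*

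**What the plan says.** **Missing data.** Protocol 9.6 and SAP 3.2 carry essentially the same sentence: missing primary-endpoint values may be filled in by maximum likelihood when that is required. The source cited in Protocol 9.6 is listed in the bibliography as a paper on iron absorption, so it does not describe the method.

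**Primary model.** Protocol 9.1.2 and SAP 8.1 use an ANCOVA of the Week 12 change on treatment, sex, weight, haemoglobin stratum and baseline haemoglobin. The SAP adds a baseline-by-stratum interaction. The table shell in SAP Appendix 1 has no Week 4 or Week 8 term. The decision rule begins "Non-inferiority will be confirmed if the upper limit of the two-sided 95% confidence interval", with a margin of 5 g/L.

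**Data available.** Protocol 7.1: "Laboratory parameters for effectiveness evaluation will be collected at screening visits (Visit 0), Visit 2, Visit 3", and also at the final visit.

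**Withdrawal.** Protocol 5.3.1 says "the patient must be excluded in the cases listed below". The list includes a worsening disease course, intolerance, non-compliance and need for other treatment. The study is open-label (Protocol 4.4.2). Protocol 5.3.1.1 calls for an early-termination visit but does not say what is done at it.

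**Analysis sets.** Protocol 9.8 states that "the ITT population will be considered to be a population for statistical analysis". The protocol's ITT set requires patients "who have hemoglobin level data both before and after treatment with the investigational product and the reference product". SAP 4.3.2 requires a dose and that the patient "completed at least one efficacy parameters evaluation visit". SAP section 1 promises conformance with the protocol, "including the definition of the analysis data sets". Both documents define a per-protocol set. The synopsis sets the target of 286 on patients "who completed the study according to protocol".

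**The concern.** A non-inferiority conclusion here depends on what is assumed for about 15% of patients. If those who leave are mostly poor responders and their earlier haemoglobin is ignored, a product that is truly worse looks closer to the reference than it is. If predicted values are inserted and counted as data, the interval is too narrow even when loss is random. Treatment is known to all, so unequal withdrawal between arms is possible and would move the estimate even with no true difference.

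The differing ITT wordings matter because they decide who needs a Week 12 value at all. If the protocol's post-treatment haemoglobin means Week 12, nobody in ITT needs one; under the SAP wording some patients may. The sample size is built on per-protocol completers while the analysis is on ITT, so a reader will want to see both. The documents do not say how the per-protocol result is to be used.

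**Working it through.** Differences are reference minus test, so a positive value means the test product is worse.

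**1. The plan's own figure.** Inputs from Protocol 9.3: SD 15, margin 5, true difference 0, power 80%, final critical value 1.976, withdrawal 15%.
- Fixed-sample normal formula: n = 2 × (15 × (1.960 + 0.842) / 5)² = 141.3, so 142 per arm; the t-based version gives 143.
- With 143 per arm, SE = 15 × √(2/143) = 1.774. Power at 1.976 is Φ(5/1.774 − 1.976) = Φ(0.843) = 80%.
- 143/0.85 = 168.2; the plan randomises 168. The figure reproduces.

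**2. Maximum likelihood on the stated ANCOVA.** In that model a patient with no Week 12 value adds no term to the likelihood, so the treatment estimate must equal the completer estimate. An EM check on one simulated data set gave −3.4816 both ways (test minus reference). The apparent SE fell from 1.810 to 1.538 once the filled-in values were counted as data.

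**3. Size of the interval error at 15% random loss.**
- Completer SE: 1.774.
- Filled in and counted: 15 × √(143/168) × √(2/168) = 1.510. Ratio 1.510/1.774 = 0.85.
- One-sided error: Φ(−1.976 × 0.85) = 4.65%, against Φ(−1.976) = 2.4%.

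This needs only the plan's figures and the assumption that the fill-in is done this way.

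**4. Withdrawal related to response, true deficit 5 g/L.** Assumed, not in the plan: correlation of Week 8 and Week 12 changes 0.6-0.8; probability of leaving rises as the Week 8 change falls. False non-inferiority = Φ((5 − 1.976 × SE − d)/SE), where d is the deficit seen in completers.
- Log-odds slope 1 per SD, Week 8 SD 13, 5% lost: d = 4.85-4.89. At 4.85, (5 − 3.505 − 4.85)/1.774 = −1.89, giving 2.9%.
- Same slope, 15% lost: d = 4.66-4.74. At 4.66, (5 − 3.505 − 4.66)/1.774 = −1.78, giving 3.7%.
- Slopes 1 to 2: about 2.8-4.0% at 5% loss and 3.4-6.6% at 15%.
- Hard cut-off (everyone below a Week 8 threshold leaves and nobody above it does): 4.0-7.1% at 5%, with other losses random up to 15%; 6.2-17.6% if all 15% leave this way. The top ends are upper bounds, because no other mechanism selects more strongly on Week 8 at the same loss.

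Other Week 8 SDs and time profiles move the graded ranges somewhat; they are illustrations.

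**5. Unequal loss, no true difference.** Shift = ρ × 15 × (λ(p₂) − λ(p₁)), with λ(p) = φ(z_p)/(1 − p).
- 10% against 20%, every loss a lowest responder: λ = 0.195 and 0.350; shift 0.155 × 15 × (0.6 to 0.8) = 1.4-1.9 g/L. This is an upper bound.
- A third of losses outcome-driven (3.3% against 6.7%): λ = 0.077 and 0.139; shift 0.062 × 15 × (0.6 to 0.8) = about 0.6-0.7 g/L.

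For scale, with 143 per arm and an observed difference of zero, the interval stops 5 − 1.976 × 1.774 = 1.49 g/L short of the margin.

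**6. What a joint model recovers (simulation, same kind of assumptions).** When withdrawal depends on recorded Week 8 haemoglobin, a likelihood model of Weeks 4, 8 and 12 returned a deficit of 4.97-5.04 and error of 2.1-2.8%. When it depends on an unrecorded later value, it returned 4.31-4.82 and 3.2-6.5%, so it is not a complete cure.

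**7. ITT wording.** The protocol needs haemoglobin before and after treatment. The SAP needs one efficacy visit, and Protocol 7.1 lists screening among the efficacy collections. Depending on the reading, the set runs from about 286 patients (Week 12 required, 15% lost) to 336 (screening counts, all dosed).

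**The case against.** **The fill-in may be sound.** Neither document ties the likelihood to the ANCOVA, so a repeated-measures likelihood using Weeks 4 and 8 is compatible with the text. This stands. A reader might infer that the clause is useless; the documents support only that its model is not stated, so step 2 is conditional.

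**ITT is the named set.** A reader might infer that the success rule has no population. Protocol 9.8 names ITT; what is lacking is a role for the per-protocol set.

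**The two ITT wordings may nearly coincide.** The visit sections of both documents use the efficacy label for Visit 4 only. If the SAP means a post-dose visit, the gap is small. Inclusion of patients with no post-baseline haemoglobin is a possible reading, not a necessary one.

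**The loss patterns may be too harsh.** Both arms take the same active substance at the same iron dose, and Protocol 2.3.4.1 reports no withdrawals on the polymaltose complex in a donor study. A two-to-one imbalance driven wholly by poor response is therefore not to be expected. This stands, and the hard cut-off figures are bounds, not forecasts.

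**A sensitivity analysis is already planned.** Protocol 9.6 has one for questionable data that cannot be corrected. It does not cover Week 12 values that were never obtained.

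**The SAP text may be incomplete.** Its numbering passes from 4.1 to 4.3 and from 6.2 to 8, so the statement that the per-protocol set has no role rests on the text available.

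**Conclusion.** The point holds as a specification gap with a better method at hand. The interval error (about 4.7% against 2.4% at 15% random loss) follows from the plan's figures if predicted values are counted as observed. The bias figures rest on assumed correlations and withdrawal patterns: realistic grading gives about 3-4% false non-inferiority at 5% loss and 3-7% at 15%, with upper bounds of about 7% and 18%. An imbalance of 10% against 20% moves the estimate by about 0.6-0.7 g/L if a third of losses are poor responders, and by at most 1.4-1.9 g/L. The ITT and per-protocol points are inconsistencies of wording to be settled before analysis; they do not show that the trial lacks a primary set. This should be changed, but it does not by itself invalidate the design.

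**What to change.** 1. Replace the fill-in in Protocol 9.6 and SAP 3.2 and 8.1 with a pre-specified likelihood repeated-measures model of haemoglobin change at Weeks 4, 8 and 12: treatment by visit, unstructured covariance, the planned baseline terms. Test the Week 12 contrast against 5 g/L, with no filled-in values.
2. Use one ITT wording in Protocol 9.8 and SAP 4.3.2: randomised, dosed, with baseline and at least one post-baseline haemoglobin. Report by arm how many patients this excludes.
3. Report the primary comparison in the per-protocol set as a pre-specified supportive analysis, and discuss any disagreement with ITT before claiming non-inferiority.
4. Add a tipping-point analysis that lowers, in steps, the Week 12 values assumed for test-arm patients without one, and report where the conclusion changes. For scale, a 5 g/L shift in 15% of the arm moves the contrast by 0.75 g/L. From an observed difference of zero, 1.49/0.15, or about 10 g/L, would be needed.
5. State in Protocol 5.3.1.1 whether haemoglobin is among the early-termination procedures. No rule on stopping treatment needs to change.

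Cost: wording, a little extra analysis and, if item 5 is answered yes, a few samples from withdrawn patients. No patients or scheduled visits are added. In simulation with 15% random loss and no true difference, power was 82-83% with the joint model against 80% for completers.
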